10.5.3. Exploratory Efficacy Analyses

Exploratory efficacy endpoints to be analyzed at Week 25, with the exception of duration endpoints or otherwise indicated, include:

- Results of the Surgical Assessment Questionnaire
- Response based on the change in the SSD of the tumor on MRI
- Duration of response based on MRI and modified RECIST 1.1-SSD
- Mean change from baseline score in the EQ-5D-5L at Week 25
- Summary of the long term subject status during the follow-up period

10.5.4. Subgroup Analyses

The primary endpoint will be also analyzed in the following subgroups of the FAS:

- Subjects with disease located in large joints (shoulder, elbow, hip, or knee)
- Subjects with disease located in the knee
- Subjects with lower extremity tumors
- Subjects with upper extremity tumors
- Subjects at sites in China
- Subjects at sites in Taiwan

10.6. Pharmacodynamic/Biomarker Analyses

Plasma will be analyzed for PDy marker, CSF-1 activity. No formal statistical analysis of PDy endpoint will be performed. Pharmacodynamic data from each assay will be listed and biological activity will be described. Blood sample collected at specified time points will be analyzed for genes possibly related to efficacy and safety of pexidartinib.

10.7. Pharmacokinetics and Exposure-Response Analyses

10.7.1. Noncompartmental Pharmacokinetic Analyses

The PK analyses will be performed on the PK analysis set. Plasma-concentration time data for pexidartinib and ZAAD-1006a will be summarized by visit and time using descriptive statistics.

Plasma-concentration data of pexidartinib and ZAAD-1006a on C1D15 (Week 3) will be analyzed for the PK analysis set for noncompartmental analysis using standard

Proprietary and Confidential Page 73 noncompartmental methods. Primary PK parameters are area under the plasma-concentrationtime curve from time 0 h to 6 h (AUC6h), peak drug concentration (Cmax), and time of maximum observed concentration (Tmax). The PK parameters of pexidartinib will be listed for each subject and summarized using descriptive statistics.

10.7.2. Population Pharmacokinetic Analyses

Plasma-concentration data from these samples will be analyzed using a population pharmacokinetic (PopPK) approach using nonlinear mixed effects modeling by pooled with other studies data to assess and characterize the inter- and intra-subject variability in PK and to identify significant covariates. These results will be analyzed and reported separately from the clinical study results.

10.7.3. Exposure-Response Analyses

Bayesian individual exposures of pexidartinib from the PopPK analysis will be used to explore relationships between exposure metrics and biomarkers and safety and efficacy endpoints. These analyses will be summarized in a separate report.

10.8. Safety Analyses

The analyses of safety will be performed on the safety analysis set. The summary and display of TEAEs will be performed.

Terminology of the Medical Dictionary for Drug Regulatory Activities (MedDRA) will be used to assign system organ class (SOC) and preferred term (PT) classification to AEs and diseases, based on the original terms entered in the eCRF.

The incidence of TEAEs will be summarized by SOC, PT, relationship to the study drug, and severity for each treatment group. A by-subject listing will be provided for those subjects who experience an SAE, including death, or experience an AE associated with early withdrawal from the study or study drug.

10.8.1. Adverse Event Analyses

TEAEs are AEs that occur, having been absent before the first dose of study drug, or have worsened in severity after the initiating the study drug. TEAEs will be coded using MedDRA and assigned grades based on NCI-CTCAE version 5.0. The number and percentage of subjects reporting TEAEs will be tabulated by the worst CTCAE grade, SOC, and PT. Similarly, the number and percentage of subjects reporting treatment-emergent SAEs will be tabulated, as well as TEAEs leading to discontinuation of study drug.

A by-subject AE (including treatment-emergent) data listing including but not limited to verbatim term, SOC, PT, CTCAE grade, and relationship to study drug will be provided. Deaths, other SAEs, and other significant AEs, including those leading to discontinuation of study drug, will be listed.

10.8.2. Clinical Laboratory Evaluation Analyses

Descriptive statistics will be provided for the clinical laboratory results by scheduled time of evaluation for the safety analysis set, as well as for the change from baseline. In addition, mean

change from baseline will be summarized for the maximum and minimum post-treatment values and the values at the end of treatment visit.

Abnormal clinical laboratory results will be graded according to NCI-CTCAE version 5.0, if applicable, and the grade will be presented in a by-subject data listing. A shift table, presenting the 2-way frequency tabulation for baseline and the worst post-treatment value according to the NCI-CTCAE grade, will be provided for clinical laboratory tests.

Abnormal clinical laboratory test results deemed of clinical significance or of Grade 3 or 4 will be listed.

10.8.3. Vital Sign Analyses

Descriptive statistics will be provided for the vital signs measurements by scheduled time of evaluation for the safety analysis set, as well as for the change from baseline. In addition, mean change from baseline will be presented for the maximum and minimum post-treatment values and the values at the end of treatment visit.

10.8.4. Electrocardiogram Analyses

Descriptive statistics will be provided for the ECG measurements by scheduled time of evaluation for the safety analysis set, as well as for the change from baseline. In addition, the number and percentage of subjects with ECG interval values meeting the criteria will be tabulated (eg, $QTc \le 450 \text{ ms}$, $> 450 \text{ to} \le 480 \text{ ms}$, > 480 ms to $\le 500 \text{ ms}$, and > 500 ms) and QTcF maximum changes from baseline (> 30 and > 60 ms) over all post-treatment evaluations will be summarized. ECG data will also be presented in the data listings.

10.8.5. Physical Examination Analyses

Physical examination data will be listed.

10.8.6. Concomitant Medication Analyses

Concomitant medications will be coded using the World Health Organization drug dictionary (most recent version). Number and percentage of subjects taking concomitant medications will be summarized for the safety analysis set.

10.9. Other Endpoint Analysis

Not applicable.

10.10. Interim Analyses

No formal interim analysis is planned.

10.11. Sample Size Determination

Planned sample size is approximately 35 subjects. The 95% CIs for some ORR values based on 35 subjects are as follows:

N	Number of responders	ORR	95% CI
35	9	25.7%	(12.5%, 43.3%)

Protocol PL3397-A-A303 Version 4.0, 29JAN2021

35	10	28.6%	(14.6%, 46.3%)
35	11	31.4%	(16.9%, 49.3%)
35	12	34.3%	(19.1%, 52.2%)
35	13	37.1%	(21.5%, 55.1%)
35	14	40.0%	(23.9%, 57.9%)
35	15	42.9%	(26.3%, 60.6%)
35	16	45.7%	(28.8%, 63.4%)

10.12. Statistical Analysis Process

The clinical study will be analyzed by DS or its agent/CRO followed by this protocol, and statistical analysis plan (SAP) which will demonstrate all methodologies and displays/shells for statistical analyses.

The SAP will provide the statistical methods and definitions for the analysis of the efficacy and safety data, as well as describe the approaches to be taken for summarizing other clinical study information such as subject disposition, demographic and baseline characteristics, study drug exposure, and prior and concomitant medications. The SAP will also include a description of how missing, unused, and spurious data will be addressed.

To preserve the integrity of the statistical analysis and clinical study conclusions, the SAP will be finalized prior to database lock.

All statistical analyses will be performed using SAS[®] Version 9.2 or higher (SAS Institute, Cary, NC 27513).

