5. STUDY TREATMENT

5.1. Assigning Subjects to Treatments and Blinding

5.1.1. Treatment Group

This is a single arm study. Eligible subjects will receive 400 mg twice daily for a total daily dose of 800 mg (2 capsules in the morning and 2 capsules in the evening).

Treatment duration of pexidartinib is presented in Section 3.1.1.

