5.1.3. Blinding

This study is open-label and no blinding will be performed for the study drug. However, all MRI images (scans) will be assessed by central readers blinded to study subject information according to procedures outlined in a separate MRI Imaging Charter.

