7.1. Primary Efficacy Endpoint

The primary endpoint will be the proportion of subjects who achieve a CR or PR of pexidartinib based on RECIST 1.1 at Week 25 by centrally reviewed MRI scan.

The RECIST 1.1 response categories are defined by the following criteria:

- Complete Response (CR) Disappearance of all tumors.
- **Partial Response (PR)** At least a 30% decrease in the sum of diameters of target tumors, taking as reference the baseline sum diameters.
- **Progressive Disease (PD)** At least a 20% increase in the sum of diameters of target tumors, using the smallest sum on study as the reference. In addition to the relative increase of 20%, the sum must also demonstrate an absolute increase of at least 5 mm. The appearance of one or more new tumors is also considered progression.
- **Stable Disease (SD)** Neither sufficient shrinkage to qualify for PR nor sufficient increase to qualify for PD.

CR and PR will define response for the primary endpoint and additional efficacy analyses.

Determination of an overall response for each time point is based on the combination of responses for target lesions, and the presence or absence of one or more new lesions. For the purpose of this protocol and in alignment with RECIST 1.1, determination of the tumor response status for each subject within 24 weeks treatment with respect to the primary efficacy endpoint is shown in Table 7.1.

To be considered a response, a tumor must meet the criteria for response and must have documented non-progression at Week 25. A tumor that achieves PR at Week 13 followed by neither sufficient shrinkage to qualify for CR nor sufficient increase to qualify for PD (ie, non-CR/non-PD/not evaluable [NE]) at Week 25 will be considered a responder for the primary efficacy endpoint.

Time Point Response at Week 13 (C4D1 visit)	Time Point Response at Week 25 (C7D1visit)	Tumor Response Status (Primary efficacy endpoint)
CR or PR	CR	Response (CR)
CR or PR	PD	Nonresponse (PD)
PR	non-CR/non-PD/non-NE ^a	Response (PR) ^b
SD	CR or PR	Response (CR or PR)
SD	SD	Nonresponse (SD)
SD	PD	Nonresponse (PD) ^c
CR, PR, SD, or NE	NE	Nonresponse (NE)
PD	Any	Nonresponse (PD)
NE	CR or PR	Response (CR or PR)
NE	SD or PD	Nonresponse (SD or PD)

 Table 7.1:
 Definitions of Response for the Primary Endpoint

CR = complete response; NE = not evaluable; PD = progressive disease; PR = partial response;

SD = stable disease

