7.1.1. Tumor Imaging

MRI (Noncontrast or follow the standard operation of the sites) of the affected joint will be performed at the study visits indicated in the Schedule of Assessment (Table 16.3). All MRI scans will be centrally read. Local evaluation of radiological response, stable disease (SD) or PD according to RECIST 1.1 will be recorded in the eCRF. The central MRI assessment report of progression status will not be provided unless requested. The Investigator will follow procedures (including instructions on proper imaging technique, and labeling) outlined in a separate MRI Procedure Manual. The results of the baseline, centrally read MRI scan will be used to qualify a subject, and all subsequent MRI scans will be read centrally.

If disease progression is indicated clinically or by local radiological assessment according to RECIST 1.1 at or after Week 13 but before Week 25, the Investigator may request a central review for evaluation of disease progression. If a central reading confirms RECIST 1.1 defined

disease progression, subject will be discontinued from the study unless the Investigator and the DS's Medical Monitor judge that the subject would potentially benefit from continued treatment with pexidartinib.

During the study, if indicated, Investigators should request confirmation of radiological disease progression by central read. Otherwise, central reading of MRI scans may be performed during or after the subject has completed the study. Details for MRI scan reads are outlined in the MRI Procedure Manual.

Subjects who terminate the study because of radiological disease progression will NOT have a follow-up MRI at their post-treatment visit.

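### Section 10.12 lets the SAP be finalised as late as an unnamed database lock in an open-label single-arm trial, leaving a few unsettled endpoint rules open to late choice (minor)

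*Combined protocol and SAP*

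**What the plan says.** Section 10.12 says that "the SAP will be finalized prior to database lock" and gives preservation of the integrity of the analysis as the reason. It assigns the statistical methods, the definitions and the handling of missing data to the SAP. Section 14.4 allows a change to the planned analysis to be documented in an amendment, in the SAP, or in both.

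On the design, Section 5.1.1 states "This is a single arm study" and Section 5.1.3 states "This study is open-label and no blinding will be performed for the study drug". Section 5.1.3 adds that "all MRI images (scans) will be assessed by central readers blinded to study subject information".

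On the flow of response data, Section 7.1.1 states: "Local evaluation of radiological response, stable disease (SD) or PD according to RECIST 1.1 will be recorded in the eCRF". It also allows that "central reading of MRI scans may be performed during or after the subject has completed the study", and says: "The central MRI assessment report of progression status will not be provided unless requested".

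On the primary endpoint, Sections 10.5.1 and 10.2 fix the full analysis set, a two-sided 95% Clopper-Pearson interval, and nonresponse for a subject without a Week 25 MRI. The Section 7.1 text, however, includes not evaluable among the Week 25 states that may follow a Week 13 PR, and says that such a tumor "at Week 25 will be considered a responder for the primary efficacy endpoint". Table 7.1 classes not evaluable at Week 25 as nonresponse.

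**The concern.** Finalising a SAP before lock protects an analysis mainly while treatment or outcomes are concealed from its authors. Here every subject is known to be on drug and there is no comparator, so each recorded response is already a treatment result. Any rule still open when the SAP is written could then be settled by someone who knows, at least from the local reads, which way it moves the estimate. What is at stake is the credibility of the response rate and its interval where they depend on such a rule. The secondary endpoints with unfinished definitions are exposed in the same way.

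**Working it through.** **Step 1. Can outcomes exist before the SAP must be final?**

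- The first on-treatment MRI is at Week 13 and the second at Week 25 (Table 16.3). Local RECIST results from both enter the eCRF (Section 7.1.1).
- The primary cutoff comes after every subject has completed Week 25 or discontinued (Section 10.3). All primary-endpoint scans can therefore exist before the data are locked.
- Treatment and assessment continue after the primary analysis (Section 3.1.1), so more than one lock is possible. Section 10.12 does not say which it means.
- The stated blinding covers the central MRI readers and, when possible, the range-of-motion assessor (Sections 5.1.3 and 7.2). No section withholds accumulating responses from the sponsor or the SAP authors.

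**Step 2. What is already fixed?** RECIST 1.1 at Week 25 by blinded central review, the full analysis set, the Clopper-Pearson interval, and nonresponse for a missing Week 25 MRI (Sections 7.1, 10.2 and 10.5.1). A late SAP could change these only by departing visibly from the protocol.

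**Step 3. What is still open?**

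| Rule | Where | State | Endpoint affected |
|---|---|---|---|
| PR at Week 13, not evaluable at Week 25 | 7.1 text against Table 7.1 | Text: responder; table: nonresponse | Primary |
| CR at Week 13, PR or SD at Week 25 | Table 7.1 | No row | Primary |
| Duration of response: censoring date; surgery, new therapy or death | 10.5.2 | Not given | Secondary |
| PROMIS scoring across two different item sets that are combined | 7.2.2, 16.2 | Not given | Secondary |

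The first two also carry over to response by TVS and by SSD, which are to be determined in a similar way (Sections 7.2 and 3.1.2.3). The second should be rare. From a nadir of zero, regrowth of 5 mm or more, or any new tumor, already meets the Section 7.1 definition of progression.

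**Step 4. Size of the not-evaluable rule.** The inputs are n = 35 and the interval table in Section 10.11. For x responders, the Clopper-Pearson limits are the 2.5% quantile of Beta(x, n − x + 1) and the 97.5% quantile of Beta(x + 1, n − x). All eight rows of the plan's table (x = 9 to 16) reproduce to 0.1 point; for example, 13/35 = 37.1% (21.5%, 55.1%).

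One reclassified subject moves the rate by 1/35 = 2.9 points. The documents do not say how many subjects would be affected. Assume 13 responders under Table 7.1 and k further subjects with PR then not evaluable, counted as responders under the Section 7.1 text:

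| k | Responders | Rate | 95% CI |
|---|---|---|---|
| 0 | 13/35 | 37.1% | 21.5% to 55.1% |
| 1 | 14/35 | 40.0% | 23.9% to 57.9% |
| 2 | 15/35 | 42.9% | 26.3% to 60.6% |
| 3 | 16/35 | 45.7% | 28.8% to 63.4% |

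Each step raises the lower limit by 2.4 or 2.5 points. Three subjects amount to 3/35 = 8.6 points. If k is zero, the rule changes nothing.

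**The case against.** The strongest reply is that little is left to choose. The population, estimator, interval and missing-scan rule are in the protocol, no interim analysis is planned, and there is no null rate or success threshold to aim at. The primary reads are made by blinded readers, and the central progression report goes out only on request. The local reads in the eCRF feed exploratory endpoints. This stands, and it confines the point to the open rules.

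The not-evaluable conflict also looks like a drafting slip. The sentence describes a scan that shows too little shrinkage for CR and too little growth for PD, which an unevaluable scan cannot show. The sentence before it requires documented non-progression at Week 25, and two rows of Table 7.1 agree with nonresponse. This largely stands, and it is why the sentence should be corrected directly, whatever the SAP date. It does not close the matter while the text is unchanged, because footnote b of Table 7.1 treats a PR as ongoing until progression is documented, so the other reading can still be argued.

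Finally, the deadline is only a latest date. The documents give no SAP date and no separate SAP text, so the SAP may have been finished early and may settle every rule listed. That is true. The point concerns what the protocol permits.

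**Conclusion.** The point holds as a minor one. The protocol permits the SAP to be finalised after responses are known, and two gaps in the primary responder derivation and two secondary definitions are unsettled in the protocol. The 2.9 points per subject is an illustration at the planned 35 subjects; any total depends on an assumed count.

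A reader might infer more, and the documents do not support it:

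- That the rules were or will be written with the outcomes in view. Nothing shows that anyone looked, or when the SAP was signed.
- That the safeguard fails altogether. The main primary choices are fixed in the protocol, and central reading is blinded.
- That a definite amount of the response rate is at risk. The range of 1 to 3 subjects is assumed, and the weight of the text favours nonresponse.
- That PROMIS scoring or censoring dates could raise the response rate. They cannot.
- That type I error is inflated. With no hypothesis test or success threshold, no such figure can be computed.

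**What to change.** 1. In Section 7.1, change the Week 25 description from not evaluable to non-NE, in line with Table 7.1 and the requirement for documented non-progression. Add a row to Table 7.1 for CR at Week 13 followed by PR or SD at Week 25.
2. Replace the Section 10.12 sentence with: *The SAP, including the responder derivation, the PROMIS scoring and the censoring rules, will be finalised before any post-baseline central read is released to the sponsor or the SAP authors, ideally before the first Week 13 assessment.* A Week 25 milestone would be too late, because Table 7.1 uses Week 13 responses. If that date has passed, finalise the SAP before central reads are transferred or any post-baseline response data are tabulated, and state who had access to response data.
3. Name the lock meant, which should be the one for the primary analysis, and label later changes as post hoc in a dated amendment.

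The cost is that SAP work moves forward and late changes need an amendment. No extra data are required.

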11. DATA INTEGRITY AND QUALITY ASSURANCE

The Investigator/investigational study sites will permit study-related monitoring, audits, IRB review, and regulatory inspections by providing direct access to the source data/documents. Direct access includes permission to examine, analyze, verify, and reproduce any records and reports that are important to the evaluation of a clinical study.

11.1. Monitoring and Inspections

DS/CRO monitor and regulatory authority inspectors are responsible for contacting and visiting the Investigator for the purpose of inspecting the facilities and, upon request, inspecting the various records of the study (eg, CRFs, source data, and other pertinent documents).

The verification of adherence to the protocol; completeness, accuracy, and consistency of the data; and adherence to ICH GCP and local regulations on the conduct of clinical research will be accomplished through a combination of onsite visits by the monitor and review of study data remotely. The frequency of the monitoring visit will vary based on the activity at each study site. The monitor is responsible for inspecting the eCRFs and ensuring completeness of the study essential documents. The monitor should have access to subject's medical records and other study-related records needed to verify the entries on the eCRFs. Detailed information is provided in the monitoring plan.

The monitor will communicate any deviations from the protocol, Standard Operating Procedures, GCP and applicable regulations to the Investigator and will ensure that appropriate action (s) designed to prevent recurrence of the detected deviations is taken and documented.

The Investigator agrees to cooperate with the monitor to ensure that any problems detected in the course of these monitoring visits are addressed to the satisfaction of DS and documented.

In accordance with ICH GCP and the DS's audit plans, this study site may be selected for audit by representatives from DS. Audit of study site facilities (eg, pharmacy, drug storage areas, laboratories) and review of study related records will occur in order to evaluate the study conduct and compliance with the protocol, ICH GCP, and applicable regulatory requirements. The Investigator should respond to audit findings. In the event that a regulatory authority informs the Investigator that it intends to conduct an inspection, DS shall be notified immediately.

11.2. Data Collection

DS or its designee will provide the study sites with secure access to and training on the EDC application, sufficient to permit site personnel to enter or correct information in the eCRFs for the subjects for which they are responsible.

eCRFs will be completed for each study subject. It is the Investigator's responsibility to ensure the accuracy, completeness, clarity, and timeliness of the data reported in the subject's eCRF.

The Investigator, or designated representative, should complete the eCRF as specified in the eCRF Completion Guidelines.

The audit trail entry will show the user's identification information, and the date and time of the correction. The Investigator must provide through the EDC application formal approval of all

the information in the eCRFs and changes to the eCRFs to endorse the final submitted data for the subject for which he or she is responsible.

DS or a designee will retain the eCRF data and corresponding audit trails. A copy of the final archival eCRF in the form of a compact disk or other electronic media will be placed in the Trial Master file.

